1 DEFINITIONS AND ABBREVIATIONS

Term	Description
ADE	Adverse Device Effect
AE	Adverse Event
AMDT	Approved Medical Device on Test
AMEI	Active Middle Ear Implant
CER	Clinical Evaluation Report
CIP	Clinical Investigation Plan
CIR	Clinical Investigation Report
CRF	Case Report Form
CRO	Contract Research Organisation
CT	Computed tomography
DCF	Data Clarification Form
DD	Device Deficiency
EC	Ethics Committee Synonymous abbreviations/terms include: IRB (Institutional Review Board) IEC (Institutional Ethics Committee or Independent Ethics Committee) HREC (Human Research Ethics Committee)
eCRF	Electronic Case Report Form
EDC	Electronic Data Capture
GCP	Good Clinical Practices
HL	Hearing loss
HP	Hearing Preservation
IB	Investigator's Brochure
ICF	Informed Consent Form
IDMC	Independent Data Monitoring Committee
IMD	Investigational Medical Device
NCA	National Competent Authority
PI	Principal Investigator
PIL	Principal Investigator List
PMS	Post-Market Surveillance
RW	Round window
SADE	Serious Adverse Device Effect
SAE	Serious Adverse Event
SAP	Statistical Analysis Plan

Term	Description
SNR	Signal-to-noise ratio
SOP	Standard Operating Procedure
UADE	Unanticipated Adverse Device Effect
USADE	Unanticipated Serious Adverse Device Effect

2 CLINICAL INVESTIGATION SYNOPSIS

Investigation title	A prospective, single-centre evaluation of Carina microphone sensitivity and maximum stable gain in adult recipients
Short title	CAMSEN
Investigation number	AI-5770
Name of Approved Medical Device on Test	Cochlear™ Carina® 2 System MET-7000
Intended use of investigational medical device(s) AMDTs for adults	The Carina Fully Implantable Middle Ear Implant System MET-7000 with the MET-7500 actuator is intended to compensate auditory deficits in individuals aged 14 or older with moderate to severe sensorineural hearing loss, and for moderate to severe conductive or mixed hearing loss when used with one of the actuator extensions. The system provides amplification via direct mechanical stimulation of the auditory system.
Name and description of comparator device/product(s)	Not applicable
Expected start date (first subject consented)	January 2020
Expected enrolment period	2 months
Expected duration per subject	1 day
Expected total duration of the clinical investigation	2 months
Number of subjects planned	Up to 20 subjects will be enrolled.
Number of investigational sites planned	Single site
Inclusion criteria	
 1. Eighteen years of age or older at the time of enrolment in the study 2. Current recipient of a Cochlear Carina System.
Exclusion criteria	
 1. Unwillingness or inability of the candidate to comply with all investigational requirements as determined by the Investigator

Objectives and Endpoints	
Objectives	Endpoints
1. To characterize Carina microphone sensitivity	Acoustic sensitivity of implanted microphone [dB FS for 0.1 Pa], in-situ, for audiometric frequencies 250-6000 Hz, median and percentiles
2. To characterize Carina microphone : accelerometer ratio for acoustic stimulation	Ratio [dB] of response of implanted microphone to response of implanted accelerometer, in-situ, for audiometric frequencies 250-6000 Hz, median and percentiles
3. To characterize Carina microphone impulse response for acoustic and actuator stimulation	Identification of the system's acoustic and vibration transfer functions including non-linear components.
4. To characterize Carina maximum stable gain.	Transfer function from Carina output to actuator [dB FS] to Carina input from implanted microphone [dB FS], for audiometric frequencies 250-6000 Hz, with and without plugged ear canal

3 SCHEDULE OF EVENTS

Visit Type	Screening	Visit
Timing of Investigation		
Visit window (±)		
Procedures		
Written informed consent	X	
Eligibility	X	
Audiogram (bone conduction)		X
Direct thresholds		X
Microphone sensitivity		X
Microphone impulse response		X
Maximum stable gain		X
Adverse Events		X

4 BACKGROUND INFORMATION AND RATIONALE

4.1 Introduction and Study Rationale

The totally implanted Carina System is an active middle ear implant where all components (microphone, signal processing electronics, power source, and middle ear actuator) are implanted under the skin, making the system invisible and compatible with occupations and lifestyles that involve exposure to humidity or dust.

Placing a microphone under the skin affects its acoustic sensitivity and vibration sensitivity. With higher vibration sensitivity of the microphone, it may pick up small vibrations of the skull caused by the actuator coupled to a middle ear ossicles, which may lead to feedback squealing, similar to a conventional hearing where an acoustic feedback pathway from speaker to microphone may led to feedback squealing.

So far, acoustic sensitivity of an implanted microphone has been measured in bench and cadaver studies, and in a very small number of subjects implanted with a percutaneous access to the microphone (Gérard et al., 2017). Now, software is available to enable non-intrusive microphone measurements in existing patients with the Carina device, through a wireless link to the implant.

Detailed knowledge of the acoustic sensitivity of the implanted microphone, and its inter-individual variability, will allow more accurate calculation of overall system performance, and thereby more accurate prediction of clinical outcomes.

Detailed knowledge of the vibration sensitivity and the ratio of acoustic to vibration sensitivity will help to optimize future signal processing strategies intended to reduce the perception of body sounds, and the to reduce feedback.

Clinical studies on device performance typically report speech intelligibility scores and aided thresholds or functional gain, but it cannot be inferred to what extend the observed functional gain is determined by audiological needs, or the subject's preferences, or device limitations. With the research software available now, an objective measurement of the feedback transfer function and thereby of maximum stable gain can be made, which is independent of the audiological profile of the individual study subject, and their listening preferences.

Detailed knowledge of objectively measured maximum stable gain, and its inter-individual variability, will allow more accurate calculation of overall system performance, and thereby more accurate prediction of clinical outcomes.

4.2 Findings of Previous Nonclinical and Clinical Studies

4.2.1 Nonclinical Data

n/a

4.2.2 Clinical Data

The performance with an implanted microphone was compared to a standard external sound processor, in one patient fitted with temporary percutaneous access to the microphone (Jenkins & Uhler, 2012). A similar study on 4 subjects, also fitted with temporary percutaneous access to the microphone, was reported by (Gérard et al., 2017). Neither study investigated the sensitivity of the acceleration sensor. Maximum stable gain could also not be measured, because those were cochlear implant recipients, not recipients of an active middle ear implant.

5 MEDICAL DEVICE INFORMATION

5.1 Identity and Description of the Approved Medical Device on Test (AMDT)

The intended purpose of the Carina System for adults is to compensate auditory deficits in individuals aged 14 or older with moderate to severe sensorineural hearing loss, and for moderate to severe conductive or mixed hearing loss when used with one of the actuator extensions. The system provides amplification via direct mechanical stimulation of the auditory system.

As shown in Figure 1, the Carina System consists of a main implant body, containing the signal processing electronics and rechargeable battery, the pendent with the implantable microphone, and an output actuator intended to be coupled to a middle ear ossicles or the cochlea.

Figure 1: Carina implant, composed of the main implant body with electronics and battery (top), the implantable microphone pendent (middle), and the MicroDrive™ actuator (bottom).

5.2 Identity and Description of the Comparator

There is no comparator in this study.

5.3 Accessory Device Requirements

The AMDT is used in conjunction with the Carina Charging System (composed of the Carina Charger Base AUD-5112, the Carina Charger Body AUD-5111 and the Carina Charging Coil AUD-5120), the Carina Remote Control AUD-5900, and optionally the Carina Button Processor BAP-11x0.

During the measurements, the implant will be controlled using Carina 2 Surgical & Fitting Software (CE marked) via the Carina Interface SUR-2300 and the Carina Interface Coil SUR-2320.

6 OBJECTIVES

6.1 Objectives

Since this study is a pilot investigation without powering to reject specific null hypotheses, objectives and associated endpoints in section 9.2 are listed without differentiation between primary and secondary objectives.

1. To characterize Carina microphone sensitivity, in-situ, and its variability
2. To characterize the ratio of (a) microphone response to sound to (b) accelerometer response to sound, in-situ, and its variability
3. To characterize Carina microphone impulse response for acoustic and actuator stimulation
4. To objectively measure maximum stable gain, i.e. gain before feedback squealing would occur

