7.3.2 Maximum stable gain

Measurement of microphone and accelerometer signal (spectrum and impulse response) in response to a stimulus generated by the implanted actuator, as defined in D1673818.

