8.3 Risks Associated with Participation in the Clinical Investigation

The clinical trial does not prescribe medical treatments. No interaction with medication that may be given as part of clinical routine is anticipated.

Theoretically, the stimulation of the patient's cochlea with the white noise signal used to measure maximum stable gain could damage residual hearing, if it was dangerously loud. The maximum stimulation level that can be set in the software is 85 dB MET (broadband), which is a -35 dBV drive level to the actuator (Jenkins, Pergola, & Kasic, 2007). Actuator efficiency as measured in temporal bone studies and clinically (Grossöhmichen et al., 2017) is below 120 dB SPLeq @ 1V median, so the -35 dBV corresponds to 85 dB SPLeq loudness perceived by the patient. Even at exceptionally good actuator efficiency of 125 dB SPLeq @ 1V, equivalent loudness will be below (125-35) = 90 dB SPLeq.

A stimulation level of 91 dB SPL is deemed safe for a maximum of 2 hours per day continuous exposure, it is the maximum acceptable loudness dosage for workplace noise hazards (NIOSH, 1998), below which an employer is not even required to offer hearing protection. The planned measurement duration (see below) is 2 conditions x 3 repetitions x 10s = 60s, far below the 2h limit.

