9.2 Endpoints

1. Acoustic sensitivity of implanted microphone [dB FS for 0.1 Pa], in-situ, for audiometric frequencies 250-6000 Hz, median and percentiles
2. Ratio [dB] of response of implanted microphone to response of implanted accelerometer, in-situ, for audiometric frequencies 250-6000 Hz, median and percentiles
3. Transfer function from Carina output to actuator [dB FS] to Carina input from implanted microphone [dB FS], for audiometric frequencies 250-6000 Hz, with ear canal open and ear canal plugged
4. Identification of the system's acoustic and vibration transfer functions including non-linear components.

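### Does the plan need a microphone-to-accelerometer ratio under actuator stimulation as well as under sound?

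*Combined protocol and SAP*

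**What the plan says.** Section 6.1 states objective 2 as "To characterize the ratio of (a) microphone response to sound to (b) accelerometer response to sound, in-situ, and its variability". The synopsis agrees: "To characterize Carina microphone : accelerometer ratio for acoustic stimulation". The matching endpoint in section 9.2 is "Ratio [dB] of response of implanted microphone to response of implanted accelerometer, in-situ, for audiometric frequencies 250-6000 Hz, median and percentiles"; it names no stimulus.

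The other endpoints, in the numbering of section 9.2, are:

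- endpoint 1: the microphone's acoustic sensitivity;
- endpoint 3: the path from actuator output to microphone input, "with ear canal open and ear canal plugged";
- endpoint 4: identification of acoustic and vibration transfer functions, with no sensor, frequency set or summary named.

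The synopsis pairs endpoint 4 with objective 3, the microphone impulse response under acoustic and actuator stimulation.

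Section 4.1 gives the motive. It wants the response to vibration known in detail, and it expects that "the ratio of acoustic to vibration sensitivity will help to optimize future signal processing strategies intended to reduce the perception of body sounds". Less feedback is a further aim named there. Section 4.2.2 says of the two earlier studies: "Neither study investigated the sensitivity of the acceleration sensor". Section 7.3.1 records both sensors in response to external sound. Section 7.3.2 does the same for the actuator: "Measurement of microphone and accelerometer signal (spectrum and impulse response) in response to a stimulus generated by the implanted actuator". Both sections refer to measurement document D1673818, which is not among the documents reviewed.

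**The concern.** A ratio whose numerator and denominator are both responses to sound contains no response to vibration. It shows how much wanted sound reaches the accelerometer, which is useful. It does not show how the two sensors compare when the skull is driven by the actuator. A reader who takes the acoustic-to-vibration relation in section 4.1 to mean the accelerometer-referenced ratio under each stimulus finds only one of the two ratios among the endpoints.

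Endpoint 3 uses the actuator, but its reference is the electrical drive and not a measured vibration. Endpoint 4 might supply the rest, but only if it is read to include the accelerometer. At stake would be whether the second ratio, and its spread between recipients, is reported at all, or whether that is decided after the data are seen.

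**Working it through.** The plan gives no sensor responses, standard deviations or sample size calculation, so it has no figure to reproduce. The check sets sections 7.3.1, 7.3.2 and 9.2 side by side.

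**Coverage.** Write M and A for microphone and accelerometer response in dB, with subscript s for sound and v for actuator.

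| Cell | Recorded under | Named in section 9.2 |
|---|---|---|
| M_s | 7.3.1 | endpoint 1; also endpoint 2 |
| A_s | 7.3.1 | endpoint 2, within the ratio |
| M_v | 7.3.2 | endpoint 3 |
| A_v | 7.3.2 | not by name; endpoint 4 if read broadly |

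All four cells are recorded, and three of them enter an endpoint that names the sensor.

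**What can be derived.** The sound ratio is R_s = M_s − A_s (objective 2). The actuator ratio would be R_v = M_v − A_v. The difference is

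R_s − R_v = (M_s − M_v) − (A_s − A_v).

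Endpoints 1 and 2 give A_s = M_s − R_s for each subject, and endpoint 3 gives M_v relative to drive. Only A_v is left, and it is in the recordings of section 7.3.2. No further stimulation is needed: section 8.3 budgets the maximum-stable-gain stimulus at "2 conditions x 3 repetitions x 10s = 60s", and A_v comes from the same actuator recordings.

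**Is the stimulus of endpoint 2 in doubt?** The synopsis table sets this endpoint against an objective limited to acoustic stimulation, and section 6.1 says sound for both sensors. The silence in section 9.2 is therefore settled elsewhere in the same document.

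**What section 4.1 asks for.** It introduces acoustic and vibration sensitivity as two properties of a microphone placed under the skin. The sentence on their ratio does not mention the accelerometer. On that reading the comparison is M_s against M_v, covered by endpoints 1 and 3 and by objective 3. Objective 4 also needs M_v only, because the feedback loop runs from actuator to microphone and the accelerometer is not part of it.

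**Size, by assumed values.** Take R_s = 20 dB and let R_v lie between −10 and +10 dB; neither value is from the documents. The difference runs from 20 − (−10) = 30 dB to 20 − 10 = 10 dB while R_s stays fixed. This shows that R_s does not determine R_v. It does not show that any planned result is wrong.

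A second illustration supposes one fixed ratio used to subtract vibration in every recipient. A gain error of e dB leaves 20·log10|1 − 10^(e/20)|:

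- e = +1 or −1: −18.3 or −19.3 dB;
- e = +3 or −3: −7.7 or −10.7 dB;
- e = +6 or −6: 0.0 or −6.0 dB.

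The plan describes no such algorithm, so these values concern a possible later design and not this study.

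**Precision.** Under normality, the 95% limits for a between-subject SD are √((n−1)/χ²) times the estimate: 0.76 to 1.46 for n = 20 and 0.69 to 1.83 for n = 10. The half-width for a mean is t(0.975, n−1)/√n: 0.468 SD for n = 20 and 0.715 SD for n = 10. These factors hold for any per-subject quantity in this study, and naming another endpoint does not change them.

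**The case for a change.** The best argument for a change is that endpoint 3 does not measure vibration sensitivity in the strict sense. It is relative to electrical drive, and drive need not produce the same vibration in each recipient. Section 8.3 itself allows actuator efficiency to vary, from a median below 120 to an exceptional 125 dB SPLeq at 1 V, a gap of more than 125 − 120 = 5 dB. Those figures describe output to the cochlea and not skull vibration, but they suggest that drive is an imperfect reference. The accelerometer would be a better one. Endpoint 4 is paired with an objective that names the microphone only, so it need not include the accelerometer. The plan has no exploratory endpoints to catch the quantity, and naming it would cost one table.

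Much of this stands. No endpoint commits the study to R_v, and endpoint 4 is loosely worded. An accelerometer-referenced ratio would be informative. But that argues for an additional quantity, not for correcting one already planned. Section 4.1 describes what the knowledge may later be used for; the four objectives are in section 6.1, and none promises R_v. The remark in section 4.2.2 on earlier studies is already answered in part by objective 2, which brings in accelerometer data. The worry about choices made after seeing the data has little force here: sections 9.1 and 9.3 provide descriptive summaries only and no hypotheses, so there is no error rate to inflate.

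**Conclusion.** No change is needed. The observation about the text is correct: the ratio is specified for sound only, and no endpoint names it under actuator stimulation. But the plan as written yields valid descriptive results for all four stated objectives. One of four sensor-by-stimulus cells lacks a named endpoint, and it is still recorded. An analyst who wants the actuator ratio can compute it per subject, by frequency, from existing data and report it with the same summaries. The effect on stated numbers, precision and conclusions is nil.

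This rests on three assumptions: that the recordings under sections 7.3.1 and 7.3.2 are made as described; that section 4.1 refers to the microphone's own two sensitivities, which is the more natural reading but not the only one; and that the results remain descriptive. D1673818 may already define the sensors and derived quantities. That could not be checked, and the conclusion does not depend on it.

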6.2 Exploratory Objective

There are no exploratory objectives.

7 DESIGN OF THE CLINICAL INVESTIGATION

7.1 General

The investigation is a single-centre, prospective, single-arm, post-market, non-interventional, pilot clinical investigation in adults previously implanted with the Carina system.

The subjects will include men and women aged 18 years and over.

Subjects will attend one scheduled study visit to be assessed as described in the CIP Schedule of Events (section 3). At the study visit, several objective acoustic measurements will be performed that do not require active participation from the subject. No data monitoring committee will be used for this clinical investigation.

7.1.1 Design Rationale

The single-subject repeated measures, pilot design will enable an estimation of microphone sensitivity and maximum stable gain.

7.2 Subjects

Written, informed consent must be obtained from subject before initiating any study procedures which are not part of clinical routine.

Other than meeting the inclusion criteria stated below, subjects will be recruited into the study; with no pre-selection based on age (other than being an adult, 18 years-of-age or older), ethnicity or gender.

7.2.1 Inclusion Criteria

Subjects must meet all of the inclusion criteria described below to be eligible for this clinical investigation.

1. Eighteen years of age or older at the time of enrolment in the study
2. Current recipient of a Cochlear Carina System.

7.2.2 Exclusion Criteria

Subjects who meet any of the exclusion criteria described below will not be eligible for this clinical investigation.

1. Unwillingness or inability of the candidate to comply with all investigational requirements as determined by the Investigator.

7.2.3 Number of Subjects Required

Up to 20 subjects will be enrolled, which is the total number of patients implanted at the investigational site at the time of writing of this document.

Since the study is a pilot investigation, sample size calculations have not been conducted.

7.2.4 Vulnerable Populations

Not applicable.

7.2.5 Enrolment & Study Duration

The preoperative assessment will be composed of one evaluation. The ICF must be signed prior to any study related evaluation taking place.

The enrolment period for the clinical investigation is anticipated to be 1 month from the time of first subject consent to enrolment of the last subject.

The expected duration of each subject's participation in the clinical investigation, is 1 month, from the time of informed consent through to the only study visit.

The anticipated total duration of the clinical investigation is therefore 2 months.

Clinical Investigation completion is last subject visit completed. In the event of an ongoing SAEs/SADEs at the time of this last visit, the clinical investigation completion will be extended for a further 30 days, or until resolution or stabilisation of the event, whichever comes first.

7.2.6 Criteria for Subject Withdrawal

Subjects can decide to withdraw from the investigation at any time. The Investigator shall ask the reason(s), although the subject does not have to give a reason. If a reason for withdrawal is offered, it should be documented in the subject's source files and the case report form (CRF).

The Investigator or Sponsor may also decide to withdraw a subject from the clinical investigation if it is considered to be in their best interests.

Subject withdrawal may be for any of the following reasons:

- Adverse Event (AE)
- Device Deficiency (DD)
- CIP or GCP deviation
- Subject lost to follow-up
- Subject withdrew consent
- Subject death
- Sponsor decision
- Investigator decision
- Other (specify)

If a subject is lost to follow-up, every possible effort must be made by the study site personnel to contact the subject and determine the reason for discontinuation. It must be remembered however that the subject does not need to provide a reason/s. At least 3 separate attempts taken to contact the subject must be documented.

Enrolled subjects who are withdrawn/discontinued will not be replaced.

7.2.7 Randomisation Procedures

Not applicable

7.2.7.1 Blinding Procedures

Not applicable in this pilot study with no comparator.

7.2.8 Post-investigation Medical Care

Not applicable

7.3 Performance Evaluations and Procedures

7.3.1 Microphone sensitivity and impulse response

Measurement of microphone and accelerometer signal (spectrum and impulse response) in response to an external sound, as defined in D1673818.

